1.4.2.5 PRO 140 2301 Study

PRO 140 2301 was a multi-center, randomized, double-blind, placebo-controlled, parallel group study in 30 male and female adult subjects infected with HIV-1. Subjects were randomized to one of three groups (N=10/group), each receiving one of three treatments: (i) a single IV dose of 5 mg/kg by 30-minute IV infusion; (ii) a single IV dose of 10 mg/kg by 30-minute IV infusion; (iii) a single placebo dose by 30-minute IV infusion. The objective of the study was to assess and characterize the PK and PD of PRO 140 administered by IV infusion, assess efficacy at a new dosage level, and safety and tolerability of single doses of PRO 140.

All PRO 140-treated subjects had more than 10-fold reduction in viral loads (mean max \log_{10} reductions were 1.83 for treatment groups and 0.32 for placebo) (Figure 1-4). Both the 5 mg/kg and 10 mg/kg doses have shown favorable tolerability and no dose-limiting toxicity has been observed. High levels of receptor occupancy (>85% reduction in the number of cells detected) were observed for 29 days after treatment with both 5 and 10 mg/kg doses.

Figure 1-4: PRO 140 2301 Study: Mean change from baseline in HIV-1 RNA (\log_{10} copies/mL) over Time (ITT Subjects)

1.4.2.6 PRO 140 2101 Study

A subcutaneous (SC) form of PRO 140 was tested in HIV-infected subjects. The trial was a randomized, double-blind, placebo-controlled study in subjects (n=44) with early-stage, asymptomatic HIV infection, only CCR5 HIV-1 detectable, and no antiretroviral therapy for 12

weeks [Thompson, 2009]. Placebo (n=10) and three PRO 140 doses were examined: 162mg weekly for three weeks (n=11), 324mg weekly for three weeks (n=11), and 324mg biweekly (every other week) for two doses (n=12). Subjects were followed for 44 days after the final dose. The study enrolled 40 males and 4 females. The median age, weight, CD4⁺ cell count and HIV-1 RNA at baseline were 42.3 years, 79.1 kg, 410 cells/ μ L and 20,000 copies/mL, respectively. Baseline characteristics were similar for the different treatment groups.

Potent, dose-dependent and highly statistically significant antiviral activity was observed (Figure 1-5 and Figure 1-6). The 324mg weekly dose resulted in a mean 1.65 log₁₀ reduction in viral load, and highly significant reductions were observed for the other dose groups as well (Figure 1-5). There was no viral rebound between 324mg doses, and the antiviral effects persisted for one week after the final dose (Figure 1-6). The trial established the first antiviral proof of concept for a long-acting, self-administrable drug for HIV-1 infection [Thompson, 2009].

Figure 1-5: PRO 140 2101 Study: Mean of the maximum (nadir) log₁₀ reductions in HIV RNA

[figure not shown]
[figure not shown]

[figure not shown]
Figure 1-6: PRO 140 2101 Study: Mean change from baseline in HIV-1 RNA (Log_{10} copies/mL) over Time (ITT Subjects)

Subcutaneous PRO 140 was generally well tolerated both locally and systemically. There was no obvious dose-related pattern of toxicity. The most common adverse events (diarrhea, headache, lymphadenopathy and hypertension) were mild to moderate and self-resolving. These events are common in HIV infection and were reported with similar frequencies in the placebo and PRO 140 treatment groups. Administration-site reactions were mild, transient, and observed in a fraction of subjects. There was a trend towards increased CD4+ cell counts in subjects treated with PRO 140 (Figure 1-7). Based on its encouraging antiviral and tolerability profiles and the convenience of weekly self-administration, SC PRO 140 has been selected for further clinical development.

Figure 1-7: Change in CD4+ cell counts in subjects treated with subcutaneous PRO 140.

Subjects (n=10 to 12 per group) were randomized to received placebo weekly (Days 1, 8, 15), 162mg PRO 140 weekly (Days 1, 8, 15), 324mg PRO 140 biweekly (Days 1, 15, with placebo on Day 8), or 324mg PRO 140 weekly (Days 1, 8, 15). CD4+ cell counts were measured over time, and the median change from baseline was determined for each treatment group.

1.4.2.7 PRO 140_CD01 Study

PRO 140_CD01 study (open-label, 43 subjects, multi-center) (12-cohort 1, 28-cohort 2, 3-cohort 3) evaluated the efficacy, safety, and tolerability of PRO 140 monotherapy (350 mg subcutaneous injection weekly for up to 12 weeks) for the maintenance of viral suppression following substitution

of antiretroviral therapy in HIV-1 infected patients (with exclusive CCR5-tropic virus). Participants in this study were experienced HIV-infected individuals who were virologically suppressed on combination antiretroviral therapy. Consenting patients were shifted from combination antiretroviral regimen to PRO 140 monotherapy for 12 weeks.

Forty (43) subjects (M/F: 40/3) with median age of 55.5 years (26-72) and median CD4 T-cell count of 604.5 cells/mm³ (365-1240) were enrolled in the CD01 study. Overall, twenty-three out of 43 (54%) enrolled subjects completed 12 weeks of PRO140 monotherapy without experiencing virologic failure. Virologic failure was defined as two consecutive HIV-1 RNA levels \geq 400 copies/mL separated by at least 3 days.

Of the first 40 enrolled subjects enrolled under cohort 1 and cohort 2, three subjects were found to have Dual/Mixed (D/M) tropism [1 at baseline and 2 at the time of virologic failure] and 40 subjects were found to have exclusive CCR5-tropic virus. A letter of amendment was filed to increase the planned number of subjects from 40 to 43 subjects to compensate for the 3 Dual/Mixed subjects enrolled in the study.

All virologic failure subjects who had available lab data in both studies achieved viral suppression to < 400 HIV-1 RNA copies/mL, as well as viral suppression to 'Non Detectable' or < 50 HIV-1 RNA copies/mL after re-initiation of ART.

The by-subject analysis of PhenoSense® Entry Assay data for PRO140, maraviroc, and AMD3100 shows no significant changes in the post-treatment IC50 and IC90 values were noted when compared with baseline values in virologic failure and non-virologic failure groups of subjects.

Anti-PRO140 antibodies were not identified in any available post-treatment sample and data derived from the CD01 study further supports the favorable PRO140 PK profile data generated from both pre-clinical as well as prior Phase 1/2 clinical trials.

Safety data were analyzed for all 43 enrolled subjects. One (1) of 43 subjects experienced an SAE that was deemed not related to the study drug by the Principal Investigator. Twenty-nine (29) of 43 subjects (67%) experienced one or more adverse events (AEs) after receiving at least one dose of PRO140. The most commonly occurring AEs were infections and infestation conditions which were reported by 14 of 43 (32.5%) subjects. The majority of the reported AEs (70/87; 80.4%) were deemed either unlikely or not related to study treatment by the Investigator. Similarly, the majority of the reported AEs (72/89; 80.8%) were deemed mild in nature.

1.4.2.8 PRO 140_CD01-Extension Study

PRO 140_CD01-Extension study (open-label, 17 subjects, multi-center) seeks to evaluate the efficacy, safety, and tolerability of PRO 140 monotherapy (350 mg subcutaneous injection weekly for up to 160 weeks) for the continued maintenance of viral suppression following substitution of antiretroviral therapy in HIV patients (with exclusive CCR5-tropic virus). Participants in this study were HIV-infected individuals who were virologically suppressed on combination antiretroviral

therapy and completed the first 12 weeks of CD01 study without experiencing virologic failure. As with the CD01 study, virologic failure was defined as two consecutive HIV-1 RNA levels ≥ 400 copies/mL separated by at least 3 days. Consenting patients may remain on PRO 140 monotherapy for up to 160 weeks.

A total of 17 subjects are participating in the CD01-Extension study of which one subject was considered not eligible as subject experienced virologic failure prior to first extension treatment.

Sixteen (16) eligible subjects (M/F: 14/2) with median age of 54.9 years (26-68) and median CD4 T-cell count of 593 cells/mm³ (365-1059) were enrolled in an extension study. One patient discontinued at week 37 (with viral load of <40 copies/mL) due to relocation. Two subjects were withdrawn due to non-treatment related SAEs at week 140 and 149, respectively. One subject was withdrawn due to re-starting their ART at week 99. Two subjects withdrew consent at week 81 and 139, respectively. Five (5) subjects experienced virologic failure (VF) (two consecutive viral loads ≥ 400 copies/mL). The mean time to virologic failure was 329 days (106-691).

Five (5) subjects are currently receiving weekly 350 mg PRO140 SC monotherapy and have completed more than three years of treatment (175-198 weeks). Overall, 12 subjects completed at least one year of treatment and 9 subjects completed at least two years of treatment in this study

PRO140 was generally well tolerated, and no drug-related SAEs were observed.

This clinical study is currently ongoing.

1.4.2.9 PRO 140_CD02 Study

PRO 140_CD02 study (double blind, placebo controlled, 52 subjects, multi-center) evaluated the efficacy, safety, and tolerability of PRO 140 in combination with existing ART (failing regimen) for one week and Optimized Background Therapy (OBT) for 24 weeks in patients infected with HIV-1. The study population included 52 treatment-experienced HIV-infected adult patients with CCR5-tropic virus who demonstrated evidence of HIV-1 replication despite ongoing antiretroviral therapy with documented history of genotypic or phenotypic resistance to at least one ART drug within three drug classes (or within two or more drug classes with limited treatment options). The options may be limited as a result of drug antiviral class cross-resistance or documented treatment intolerance.

In double-blind treatment period, virally non-suppressed subjects were randomized and treated with either PRO 140 or Placebo in combination with the failing ART regimen for 7 days. The primary efficacy endpoint was proportion of participants with $\geq 0.5 \log_{10}$ reduction in HIV-1 RNA viral load from baseline at the end of the 7 day functional monotherapy period.

During the 24-week open-label period, all subjects received PRO 140 along with Optimized Background Therapy (OBT).

This clinical study is completed.

1.4.2.10 PRO 140_CD02 Open Label

PRO140_CD02 Open Label (open label, single-arm, 25 subjects, multi-center) seeks to evaluate the efficacy, clinical safety and tolerability parameters of PRO140 in combination with existing ART (failing regimen) for one week and Optimized Background Therapy (OBT) for 24 weeks. The patient population for this trial is treatment-experienced HIV-infected patients with CCR5-tropic virus and demonstrates evidence of HIV-1 replication despite ongoing antiretroviral therapy with documented genotypic or phenotypic resistance to ART drugs within three drug classes (or within two drug classes with limited treatment options).

This clinical study is currently ongoing.

1.4.2.11 PRO 140_CD03 Study

PRO 140_CD03 study (open-label, two-arm comparator, 500 subjects, multi-center) seeks to evaluate the treatment strategy of using PRO 140 SC as a long-acting single-agent maintenance therapy versus continuing combination ART for 48 weeks in virologically suppressed subjects with CCR5-tropic HIV-1 infection. The first ~150 eligible subjects were enrolled to receive PRO 140 350mg SC weekly injection in a single-arm study. Subsequently, next ~150 subjects were randomized 1:1 to PRO140 350mg (Group A) or PRO 140 525mg (Group B).

An additional ~200 subjects will be randomized 1:1 to PRO 140 525mg (Group B) or PRO 140 700mg (Group C).

This clinical study is currently ongoing.

1.4.2.12 PRO 140_CD03 Extension Study

PRO 140_CD03 Extension study (open label, 300 subjects, multi-center) seeks to evaluate the long term efficacy, safety and tolerability of PRO 140 weekly injection as long-acting single-agent maintenance therapy versus continuing combination ART in patients infected with HIV-1. The study population includes treatment-experienced HIV-infected adult patients with CCR5-tropic virus who successfully completed PRO 140_CD03 study and continue to demonstrate HIV-1 viral suppression.

This clinical study is currently ongoing.

Table 1-1: Clinical Studies with PRO 140

[figure not shown]
Protocol Number	Phase	No. of Subjects (Planned/Analyzed)	Doses	Cell line used to make PRO-140	Subject Population	Comments
PRO 140 1101	1	20/20	Single 0.1, 0.5, 2.0, or 5.0 mg/kg	Sp2/0 myeloma	Healthy	Generally well tolerated; non-immunogenic; dose-dependent coating of CCR5; significant coating of CCR5 over placebo at 0.5, 2, and 5 mg/kg
PRO 140 1102	1	20/20	Either two or three doses totaling 200 or 350 mg respectively	CHO	Healthy	Generally well tolerated; drug derived from CHO cells well tolerated also; SC administration by Autoject® 2 better tolerated than manual injection
PRO 140 1103	1	15/14	Two doses, each of 350 mg	CHO	Healthy	More AEs associated with arm injection; trend of lower exposure in arm injections; thigh and abdominal administration preferred
PRO 140 1302	1b	40/39	Single 0.5, 2.0, or 5.0 mg/kg	Sp2/0 myeloma	HIV-1 positive	Generally well tolerated; antiviral suppression maintained for approx. 10 days with higher doses; favorable tolerability and potent, dose-dependent antiviral activity provide proof-of-concept
PRO 140 2301	2a	30/31	Single 5.0 or 10.0 mg/kg	CHO	HIV-1 positive	Generally well tolerated with no dose-limiting toxicities; potent antiviral suppression maintained for approx. 20 days when administered IV at 5 or 10 mg/kg. No dose-limiting toxicities at 10 mg/kg.
PRO 140 2101	2a	40/44	Three doses of 162 or 324 mg each	CHO	HIV-1 positive	Generally well tolerated, no drug-related SAEs or dose-limiting toxicity; antiviral activity was statistically significant; two-fold exposure at higher dose; single dose demonstrated favorable tolerability, and potent, long-acting, dose-dependent antiviral activity.
PRO 140	2b	43/43	350 mg SC weekly	CHO	HIV-1 positive	Generally well tolerated, no drug-related SAEs,

Protocol Number	Phase	No. of Subjects (Planned/Analyzed)	Doses	Cell line used to make PRO-140	Subject Population	Comments
_CD01			dose for 12 Weeks of Monotherapy (total treatment duration 14 Weeks)			weekly dose demonstrated favorable tolerability, and potent, long-acting, dose-dependent antiviral activity. Data under review and results are pending publication.
PRO 140_CD01-Extension	2b	17/17	350 mg SC weekly dose for 160 Weeks of monotherapy (total treatment duration 161 Weeks)	CHO	HIV-1 positive	This clinical study is currently ongoing.
PRO 140_CD02	2b/3	50/52	350 mg SC weekly dose for up to 25 weeks in conjunction with existing ART followed by OBT	CHO	HIV-1 positive	This clinical study is completed
PRO140_CD02 Open Label	2b/3	25/2	700mg SC + existing ART for 1 week followed by 700mg SC weekly OBT for 24 weeks	CHO	HIV-1 positive	This clinical study is currently ongoing
PRO 140_CD03	2b/3	500/TBD	350 mg, 525mg, or 700mg SC weekly dose for up to 48 weeks of monotherapy	CHO	HIV-1 positive	This clinical study is currently ongoing
Pro140_CD03 Extension	2b/3	300/TBD	350mg SC weekly monotherapy dose	CHO	HIV-1 positive	This clinical study is currently ongoing

1.5 RATIONALE FOR DOSE SELECTION

The dose of 350 mg administered SC was chosen in light of a previous analysis suggesting that such a dose would be likely to provide maximal viral load suppression. In studies with antiviral agents that block viral entry through the CCR5 receptor, there is a general consensus that in order to achieve robust antiviral effects and minimize the potential for drug resistance in combination therapy, the dose of drug should result in exposures that fall on the plateau of a Maximum Drug Effect (Emax) plot.

Figure 1-8: Emax analysis of antiviral data generated with IV and SC PRO 140.

The maximal viral load reduction was analyzed with regard to drug exposure for PRO 140. Figure 1-8 above shows this relationship. Analysis shows that PRO 140 350mg weekly dose is expected to fall on the plateau of the Emax plot.

The maximal change in HIV-1 viral load from baseline was determined at any point 59 days after initiation of therapy. To allow approximate comparisons between the IV and SC doses, the overall AUC observed for repeat SC doses was conservatively estimated by multiplying the measured AUC_{0-7d} by the number of doses administered. Viral load and AUC data were fit to an Emax equation: $E = Emax \times AUC / (AUC + AUC_{50})$. The orange diamond indicates projected data for three weekly 350 mg doses based on the mean exposure observed in the PRO 140 1103 study.

It is important to note that when larger proteins (MW> 10,000) are administered SC, they initially traffic through the lymphatic system. Uptake into the bloodstream occurs after the proteins reach the thoracic duct [Nishikawa M, 2005].

In addition, based on pharmacodynamic data from our prior SC and IV studies, maximum virologic suppression is expected to be achieved with trough concentrations that equal or exceed approximately 5 µg/mL.

Finally, the mean nadir reduction in viral load achieved with 3 weekly 324 mg SC doses (1.65 log₁₀) was similar to the mean nadir reductions observed with single 5 or 10 mg/kg IV doses (1.8 log₁₀ in each case), and higher viral load reductions are expected in the present study based on the use of the 350 mg CHO formulation. Overall, several lines of evidence indicate that maximum virologic suppression will be achieved with 350 mg weekly dosing in the present study.

Majority of subjects receiving 350 mg weekly SC dosing in monotherapy setting experienced virologic failure in CD01-Extension study. Review of PRO 140 clinical data to date with 350mg SC weekly dosing, suggests no evidence of emergence of viral isolates with reduced susceptibility to PRO 140, no altered viral tropism or anti-PRO 140 antibodies formation suggesting the most likely cause of viral rebound is inadequate dosing to fully cover CCR5 receptor populations. Based on pharmacologic modeling studies, we anticipate that the 700mg dose will result in a lower fraction of study participants with trough levels below that which will ‘uncoat’ a significant number of CD4 cells (i.e., less than a certain multiple of the IC50 or IC90 for PRO 140).

As of Protocol v4.0, newly enrolled subjects will receive 700 mg. The dose of 700 mg administered SC was chosen to provide maximum viral load suppression in a heavily treatment experienced population to avoid developing resistance to current OBT therapies.

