3 STUDY DESIGN

This is an extension study, to provide continued access to PRO 140 to subjects who complete participation in PRO140_CD02 or CD02_OpenLabel and continue to receive clinical benefit and would require PRO 140 to form a viable regimen, in the opinion of the treating physician. The patient population for this trial is treatment-experienced HIV-infected patients with CCR5-tropic virus who demonstrate evidence of HIV-1 suppression after successfully completed 24 weeks of treatment in the PRO140_CD02 or CD02_Open Label study.

Subjects participating under Protocol versions 1.0-3.0 received 350 mg of PRO 140. Dose was increased from 350 mg to 700 mg weekly to provide maximum viral load suppression in a heavily treatment experienced population to avoid developing resistance to current OBT therapies.

Those that were enrolled under version 1.0-3.0 have the option of remaining on their current dose of 350mg or increasing their dose to 700 mg for the remainder of the trial.

The study is divided into three phases: Screening, Treatment Extension and Follow-up.

Screening Phase begins with signing of Informed Consent and lasts up to 21 days. All subjects will continue taking PRO 140 SC injection in addition to OBT during the Screening Phase.

Subject will enter the Treatment Extension Phase as soon as HIV-1 viral load results are available for review by Investigator. Treatment Extension Phase consists of weekly study treatment injections along with OBT. Study participants will be regularly monitored for viral load and will cease weekly study treatment injections should they experience virologic failure. Virologic failure is defined two consecutive HIV-1 RNA levels ≥ 400 copies/mL.

Note: Subjects will be allowed to continue PRO 140 with existing OBT regimen while waiting for new regimen to be constructed by the Investigator.

Subjects who experience virologic failure at any point during the Treatment Extension Phase will undergo the Virologic Failure (VF) Visit assessments and will be followed up every 4 weeks until viral suppression is achieved (i.e., plasma HIV-1 RNA levels below level of detection) or up to a maximum of 6 months after cessation of therapy if the treating physician does not feel that there is an antiretroviral regimen that will regain full viral suppression. Subjects who do not experience virologic failure, will be followed up every 2 weeks for total of 4 weeks.

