5 SUBJECT COMPLETION AND WITHDRAWAL

5.1 SUBJECT COMPLETION

- A subject who completes the Treatment Extension Phase (without virologic failure) and 4-week Non-Virologic Failure Follow-Up Phase will be considered as having completed the study.
- A subject who experiences virologic failure during the Treatment Extension Phase, undergoes the Virologic Failure (VF) Visit assessments and is followed up until viral suppression is achieved or up to a maximum of 6 months after experiencing virologic failure if the treating physician does not feel that there is an antiretroviral regimen that will regain full viral suppression will be considered as having completed the study.

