7.11.10 CCR5 Receptor Occupancy

- To assess the number CCR5 receptors on patients' CD4 cell surface. Of those CCR5 receptors, the test will also assess the number and percentage of CCR5 receptors that are covered by PRO 140.
- Frequency of testing: This assessment will be performed up to 5 times at different treatment visits. Blood will be taken prior to PRO 140 injection (trough sample) and 24-48 hours (peak sample) after the PRO 140 injection to check for CCR5 occupancy, and correlative analysis will be performed with PRO 140 PK concentration and HIV-1 RNA levels.

All laboratory reports will be reviewed by the Investigator.

Post-treatment abnormal results that are considered by the Investigator to be clinically significant will be recorded as adverse events. If the Investigator judges it necessary, testing may be repeated in order to make the determination of clinical significance. Validated, quality-controlled laboratory data will be transferred to the main database for analyses.

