7.1.1 Subject Disposition and Withdrawals

- There will be a detailed accounting of all subjects that signed the informed consent to participate in this trial. The following will be summarized: The number of subjects who are screenedThe number of subjects who received treatment
- The number of subjects who completed the study
- The number of subjects who discontinued during the study
- The reason for all post treatment study discontinuation

In addition, there will also be a listing of all discontinued subjects, which will provide the specific reason for discontinuation.

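### The SAP specifies no count of virologic failure, overall or by dose, and counts failures who finish follow-up as completers; separately, the dose rationale calls 5 of 16 failures a majority

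*Protocol*

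**What the plan says.** **Virologic failure and completion.** Protocol 8.1 and SAP 2.3.1 list virologic failure (two consecutive HIV-1 RNA values of at least 400 copies/mL) among the events that end weekly dosing. It is not an outcome measure in Protocol 8.2 or SAP 2.4. In Protocol 5.1, the sentence on subjects who fail and are then followed up ends "an antiretroviral regimen that will regain full viral suppression will be considered as having completed the study". SAP 7.1.1 tabulates "The number of subjects who completed the study", the number who discontinued, and the reasons for study discontinuation.

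**Dose.** Under Protocol 3, subjects enrolled under versions 1.0 to 3.0 "have the option of remaining on their current dose of 350mg or increasing their dose to 700 mg". SAP 2.3.1 calls the study single arm but lists the two doses in separate rows. SAP 6.8 says there are no subgroups.

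**Tropism.** SAP 7.2.3 summarises the proportion of subjects with a Dual/Mixed result, and SAP 7.2 places outcome measures on the Safety population. Protocol 7.11.7 schedules Trofile at the virologic failure visit.

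**Occupancy.** Protocol 7.11.10 says blood will be drawn "to check for CCR5 occupancy, and correlative analysis will be performed with PRO 140 PK concentration and HIV-1 RNA levels". The SAP has no section for this and no row for it in its Appendix 1 schedule.

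**Dose rationale.** Protocol 1.5 states "Majority of subjects receiving 350 mg weekly SC dosing in monotherapy setting experienced virologic failure in CD01-Extension study". It goes on to cite "no altered viral tropism or anti-PRO 140 antibodies formation suggesting the most likely cause of viral rebound is inadequate dosing". Protocol 1.4.2.8 reports "Five (5) subjects experienced virologic failure (VF", and Protocol 1.4.2.7 reports that in CD01 "three subjects were found to have Dual/Mixed (D/M) tropism [1 at baseline and 2 at the time of virologic failure".

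**The concern.** A reader of the final tables will want to know how many subjects failed and on which dose. The specified tables do not answer either question.

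The completed row would mix subjects who stayed suppressed with subjects who failed and were then followed up. The viral load summary in SAP 7.2.1 cannot stand in for a count. Missing data are not imputed (SAP 6.3) and subjects with an undefined change are excluded, so a subject who fails and leaves the treatment phase can drop out of later means. Subjects still choosing between 350 mg and 700 mg are those for whom a plain count by dose matters most. A Dual/Mixed percentage over a mostly untested population could look reassuringly small.

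The Protocol 1.5 sentence misstates a prior result in a document that investigators and IRBs read.

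**Working it through.** **1. Where a virologic failure would appear in the specified SAP tables**

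| SAP section | What it summarises | Counts failures? | By dose? |
|---|---|---|---|
| 7.1.1 Disposition | Completed, discontinued, reasons for study discontinuation | No; failures who finish follow-up are completers | Not specified |
| 7.1.7 Administration | Number and percentage injected, by week | No | Not specified |
| 7.2.1 Viral load | Raw and change in log10 RNA | No | Not specified |
| 7.2.3 Tropism | Proportion Dual/Mixed | No | Not specified |
| 7.2.4.1 Adverse events | Overall, by severity, by relationship | No | Not specified |
| 9.2 Planned tables | Headings only, including one for efficacy | No contents given | No contents given |

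A subject who fails and finishes follow-up is completed. A subject who fails and leaves follow-up early is discontinued. The same event can therefore fall in two rows, and neither row is a failure count.

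**2. Effect of the tropism denominator, using CD01**

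- Enrolled: 43. Completed 12 weeks without failure: 23. Failures are therefore at most 43 − 23 = 20 (Protocol 1.4.2.7 does not give the count).
- Dual/Mixed at failure: 2.
- Over all enrolled: 2/43 = 4.7%. Over failures: at least 2/20 = 10%.

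The same two cases give a proportion at least twice as large when the denominator is the subjects who failed.

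**3. The majority statement**

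Protocol 1.4.2.8 accounts for every eligible CD01-Extension subject: 5 failures + 1 relocation + 2 unrelated SAEs + 1 ART restart + 2 consent withdrawals + 5 still treated = 16. A majority of 16 needs 9.

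| Denominator | Result |
|---|---|
| All eligible | 5/16 = 31.3% (exact 95% CI 11.0% to 58.7%) |
| Adding the ineligible subject who failed before the first extension dose | 6/17 = 35.3% |
| All who left | 5/11 = 45.5% |
| Failed or still treated | 5/10 = 50.0% |
| Same, plus the ineligible subject | 6/11 = 54.5% |

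A Kaplan-Meier estimate gives 33.0% to 33.7%. It covers failure times compatible with the reported mean of 329 days and range of 106 to 691, with other exits censored at their stated weeks and ongoing subjects at week 175.

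The last row of the table exceeds one half only by adding an ineligible subject and dropping six exits. Pooling with CD01 gives at most (20 + 5)/43 = 58.1%, and only if every CD01 non-completer failed; the sentence names the extension alone. Counting every exit as a failure gives 11/16 = 68.8%, which is not virologic failure. The interval for 5/16 passes 50%, but the sentence reports what was observed.

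**4. What a by-dose table could show**

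The documents do not give the dose split. Purely as an illustration, with 5, 10 or 25 subjects on a dose and no failures, the upper exact 95% limit is 1 − 0.025^(1/n), which is 52%, 31% and 14%.

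**The case against.** The strongest reply is that this is a continued-access study with no comparison, no sample size and no virologic failure outcome in the protocol, so the SAP follows the protocol. All collected data are listed by subject (SAP 7), so failures can be rebuilt. Protocol 8.7.1 also promises reasons for all post-treatment discontinuations, which is wider than SAP 7.1.1 and may capture some failures. All of this stands. It limits the point to reporting and rules out any claim that data are lost, but it does not supply a count.

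A reader might infer that the SAP will pool the doses or forbids a dose split. The documents do not say so. SAP 2.3.1 lists the doses separately, and dose columns need not be a subgroup analysis under SAP 6.8. What can be said is that no by-dose display is specified.

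The missing occupancy section may be version lag. SAP 1 cites protocol version 4.0 of 13 May 2019, while Protocol 7.14 cites guidance of March 2020. That would explain the gap without closing it.

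On the background sentence, Protocol 1.4.2.8 prints the correct count, and CD01-Extension was monotherapy whereas subjects here also take OBT. Protocol 1.5 also rests 700 mg on pharmacologic modelling and on protecting OBT from resistance. A reader might infer that the miscount undermines 700 mg; the documents do not support that.

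Nor do the two CD01 Dual/Mixed results show a tropism switch under treatment. Their origin is not stated, and in study 1302 one Dual/Mixed result was traced to pre-existing virus (Protocol 1.4.2.4).

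**Conclusion.** The SAP point holds as a cheap improvement to reporting. Failures who finish follow-up would be reported as completed, no failure count or by-dose display is specified, the tropism denominator includes subjects not scheduled for testing, and the occupancy analysis in the protocol has no counterpart in the SAP. This rests on the SAP text as supplied; the efficacy heading in SAP 9.2 could be filled with such a table, but nothing says it will be.

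The Protocol 1.5 wording is a minor error: 5 of 16 (31%) is not a majority, and the statement on tropism at 350 mg needs the CD01 qualification. The choice of 700 mg is unaffected.

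A by-dose table would not show whether rebound is caused by under-dosing. Dose is self-selected among earlier enrollees, all subjects take OBT, and numbers may be very small: Protocol Table 1-1 shows 2 subjects analysed in CD02 Open Label, the 700 mg feeder study.

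**What to change.** **SAP**

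- Add one descriptive table and listing, with no test: number with virologic failure by dose at the time of failure, and person-weeks by dose. Censor person-weeks at confirmed failure, because Protocol 5.2.1 only recommends stopping and allows dosing while a new regimen is built. Let switchers contribute to each dose, and say which dose counts if a switch falls between the two qualifying values.
- Give virologic failure its own disposition row, separate from completed.
- Report Dual/Mixed results over the number tested, with the Safety population count alongside.
- Carry the Protocol 7.11.10 occupancy summary into the SAP.
- State that dose is self-selected, that numbers may be very small and that the table is descriptive only.

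**Protocol 1.5**

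- Replace the majority wording with 5 of 16 (31%), and note that two CD01 subjects were Dual/Mixed at virologic failure, origin not stated.

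**Cost.** A little more programming, on viral load, dosing, Trofile and occupancy data already planned, and one corrected passage of protocol text. The by-dose figures will be imprecise and confounded, and should be labelled so.
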